Protocol Title: Internet-based Cognitive Behavioral Therapy to Reduce Depressive Symptoms after Stroke Pilot/Feasibility Study

Short Title: Internet-based CBT for Depression after Stroke Pilot

Investigators:

[name]
[name]
[name]

Brief Description:

Stroke is one of the leading causes of death and disability in the United States, with estimated direct and indirect costs exceeding 70 billion dollars per year. Depression is common after stroke, occurring in approximately 25% of all patients. Depression has been associated with lower quality of life, higher mortality, increased healthcare utilization and higher costs. Cognitive behavioral therapy (CBT) interventions have been shown, in small studies, to both treat and prevent the development of post-stroke depression. CBT based interventions therefore have the potential to improve quality of life and reduce healthcare costs after stroke. Unfortunately, there are significant barriers to the widespread use of CBT in the stroke population, including limited access to licensed providers, high costs of treatment, and limited mobility. Alternative methods for delivering CBT have the potential to improve access and reduce costs and may make widespread dissemination of CBT based treatment possible. We aim to test the feasibility of an internet-based CBT (iCBT) program combined with a telephone/email based coaching service in patients with recent stroke. We will do this by partnering with Joyable. Joyable is an existing, commercially available iCBT program. Joyable's iCBT Program for Depression combines 42 brief online activities with a telephone/email based coaching service, which is designed to motivate and encourage individuals to complete the online modules.

Objectives:

1. Determine the feasibility of internet-based CBT in patients with recent ischemic stroke and depressive symptoms, by quantifying adherence to the program in a pilot population of 20 subjects.
2. Quantify changes in depressive symptoms and quality of life in subjects pre- and post-program participation, to provide preliminary evidence of the efficacy of internet-based CBT to improve outcomes after stroke.

Primary Outcome variables

The primary outcomes will be the number of activities in the iCBT program completed by participants and reduction in depressive symptoms, measured the 9-item Patient Health Questionnaire (PHQ-9).

Secondary Outcome variables

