- Patients without regular internet access through a computer, tablet or smartphone are excluded.
- Subjects requiring long-term inpatient nursing care are excluded. For patients enrolled as inpatients, individuals being discharged to both home and acute rehab are eligible. Individuals being discharged to a skilled nursing facility or hospice are excluded.
- Expected life expectancy less than 6 months or other inability to comply with study follow-up.
- Pregnant women and prisoners are excluded

Vulnerable populations: Children, pregnant women, fetuses, neonates, and prisoners are not included in this research study.

Sample Size: 20 subjects will be enrolled.

Accrual: The comprehensive stroke center at the Hospital of the University of Pennsylvania (HUP) is a tertiary referral center for acute ischemic stroke, with annual case volumes of approximately 600 strokes per year on the inpatient stroke service. Additionally, the stroke team sees patients in the outpatient clinic both in follow-up from their acute hospitalization and in consultation to provide second opinions for patients treated elsewhere. Due to the broad inclusion criteria of this study, it is expected that many of the patients seen, both inpatient and outpatient, will be eligible for participation in this study. We expect that we will be able to enroll 1-2 patients per week and will complete enrollment within 6 months.

Recruitment: A stroke physician evaluates all patients with acute ischemic stroke who present to HUP. All stroke team physicians will be trained investigators in this study, and they will screen patients for eligibility during routine clinical care. Study physicians will also screen for potentially eligible subjects during outpatient clinic sessions. All eligible subjects will be informed of the study, and if they are interested in participation, a study physician will obtain informed consent. The original signed consent form will be kept in the study binder. A copy of

the signed consent form will be given to the patient and another copy will be placed in the medical record.

Procedures

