We will calculate the average PHQ-9 score at enrollment and 90 days. We will compare the PHQ-9 score from enrollment to day 90. The statistical power of this test is uncertain. In Table 2 we present estimated study power (with $\alpha=0.05$) across a range of assumptions about both the change in PHQ-9 over time and the standard deviation of the difference in PHQ-9 over time. These calculations show that although this is a small pilot study, we have >80% power to detect a difference in PHQ-9 of 3 or more points across a range of assumptions. The PHQ-9 will also be administered to subjects weekly via through the Joyable program. We will examine whether there are significant changes in score over time using repeated measures analysis (generalized estimating equations, GEE) with PHQ-9 score as the dependent variable and week as the independent variable.

In an exploratory analysis, we will divide patients into two groups based on PHQ-9 at study completion (*high depression symptoms*, defined as median or above and *low depression*

symptoms, defined as below the median score). Healthcare outcomes, including modified Rankin scale, health related quality of life, and healthcare utilization will be compared across groups. We hypothesize that patients with high depression symptoms will have worse functional outcome, lower quality of life, and higher healthcare utilization. We will also divide patients into groups based on their participation in the Joyable program and compare outcomes (e.g., PHQ-9 score, quality of life, health utilization) between subjects who showed high engagement in the program and those who showed low engagement.

Table 2. Statistical Power for single sample paired t-test

SD of the Difference	Difference in PHQ-9 Pre/Post Treatment				
	1	2	3	4	5
2	61%	99%	100%	100%	100%
3	32%	85%	99%	100%	100%
4	20%	61%	92%	99%	100%
5	15%	43%	77%	95%	99%
6	12%	32%	61%	85%	96%

Data Confidentiality

Internet-based files will only be made available to personnel involved in the study through the use of access privileges and passwords. Paper-based records will be kept in a locked, secure location and only accessible to study personnel. Prior to access to any study-related information, personnel will be required to sign statements agreeing to protect the security and confidentiality of identifiable information. Whenever feasible, identifiers will be removed from study-related information.

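### Table 2 is titled a paired t-test but overstates two-sided t-test power at n=20 by up to 4.9 points, and the >80% power claim omits the SD limit it depends on

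*Combined protocol and SAP*

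**What the plan says.** The Sample Size entry reads "Sample Size: 20 subjects will be enrolled". PHQ-9 reduction is one of the two primary outcomes, and the Analysis Plan compares the score at enrolment with the score at day 90.

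The plan concedes that the power of this comparison is uncertain. It then presents power at alpha 0.05 "across a range of assumptions about both the change in PHQ-9 over time and the standard deviation of the difference in PHQ-9 over time". The grid is headed "Table 2. Statistical Power for single sample paired t-test" and covers mean differences of 1 to 5 points and SDs of the difference of 2 to 6 points. The text draws one conclusion from it: "we have >80% power to detect a difference in PHQ-9 of 3 or more points across a range of assumptions".

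Neither the n nor the sidedness behind the table is stated with it. No expected SD is chosen, and no number of evaluable subjects below 20 is considered.

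**The concern.** There are two faults.

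- **Method and label disagree.** A reader will take the printed figures as paired t-test power at the planned 20 subjects. With 19 degrees of freedom, the t-test and its normal approximation differ by several points in the middle of the power range, so the method behind the table matters.
- **The summary sentence omits its condition.** The sentence before it uses the same phrase about a range of assumptions for the whole grid, SD 2 to 6. At 3 points, the table's own entries for SD 5 and SD 6 are below 80%. Because the plan names no expected SD, the reader cannot tell which rows apply.

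This paragraph is the only statement of what the PHQ-9 comparison can detect, and a null result would be read against it.

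**Working it through.** **Inputs.** n = 20 (Sample Size); alpha = 0.05, differences δ = 1 to 5 and SDs of the difference σ = 2 to 6 (Analysis Plan and Table 2). Sidedness is not stated. Two-sided is inferred, because no one-sided calculation, t or normal, at any n from 14 to 30 matches more than 13 of the 25 cells.

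**Step 1: reproduce the printed table.** The two-sided normal approximation is

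power = Φ(δ√n/σ − 1.96) + Φ(−δ√n/σ − 1.96).

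For δ = 3, σ = 5, n = 20: δ√n/σ = 3 × 4.472 / 5 = 2.683, and Φ(2.683 − 1.96) = Φ(0.723) = 76.5%, with a negligible second term. Unrounded it is 76.53%, which prints as 77%. All 25 cells agree after rounding, with a largest gap of 0.47 points.

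**Step 2: compute the test named in the title.** For the two-sided paired t-test,

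power = P(|T| > t(0.975; n−1)), where T is noncentral t with n−1 df and noncentrality δ√n/σ.

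For the same cell the noncentrality is again 2.683, but the critical value with 19 df is 2.093 instead of 1.96, and power is 72.1%. The full grid, as printed / t-test at n = 20 (%), is:

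| SD | δ=1 | δ=2 | δ=3 | δ=4 | δ=5 |
|---|---|---|---|---|---|
| 2 | 61 / 56.5 | 99 / 98.9 | 100 / 100 | 100 / 100 | 100 / 100 |
| 3 | 32 / 29.4 | 85 / 80.7 | 99 / 98.9 | 100 / 100 | 100 / 100 |
| 4 | 20 / 18.6 | 61 / 56.5 | 92 / 88.9 | 99 / 98.9 | 100 / 100 |
| 5 | 15 / 13.6 | 43 / 39.7 | 77 / 72.1 | 95 / 92.4 | 99 / 98.9 |
| 6 | 12 / 10.9 | 32 / 29.4 | 61 / 56.5 | 85 / 80.7 | 96 / 94.2 |

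Ten cells agree after rounding. The other 15 are overstated, 11 of them by more than 2 points, and none is understated.

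**Step 3: look for another explanation.** Across n = 14 to 30, with t and normal calculations, one- and two-sided, only two combinations match all 25 cells: the normal approximation at n = 20 and the two-sided t-test at n = 22 (largest gap 0.46). The documents nowhere mention 22 subjects.

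**Step 4: find the SD limit behind the >80% claim.** Power for a 3-point difference reaches 80% at:

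| Basis | Largest SD |
|---|---|
| Normal approximation, n = 20 | 4.79 |
| t-test, n = 20 | 4.54 |
| t-test, n = 19 | 4.41 |
| t-test, n = 16 | 4.00 |

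With 20 evaluable subjects, the t-test has 80% power for differences of 2.64, 3.30 and 3.96 points at SDs of 4, 5 and 6.

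**Step 5: allow for missing day-90 scores.** The documents give no rate, so the smaller n values are assumptions. Power for 3 points (t-test):

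| Evaluable n | SD 4 | SD 5 | SD 6 |
|---|---|---|---|
| 20 | 88.9% | 72.1% | 56.5% |
| 18 | 85.0% | 67.0% | 51.6% |
| 16 | 80.1% | 61.2% | 46.5% |

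With one subject missing (n = 19), both cells printed as 85% fall to 78.5%. One of them, 4 points at SD 6, lies within the claim about 3 or more points.

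**The case against.** The normal approximation is a standard method, so the printed cells are a correct approximation under a wrong label. Replacing them changes no conclusion at n = 20. The cells above 80% are the same before and after, and both SD limits, 4.79 and 4.54, fall between the same two table rows. The sentence does not claim every assumption: of the 15 cells at 3 or more points, 13 exceed 80% under either method. The paragraph warns that power is uncertain, and the table openly prints 77% and 61%. Twenty subjects were chosen for a feasibility pilot and not derived from power. Attrition is a separate matter from how the table was calculated.

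All of this is true, and it is why the point is minor. It does not remove it. The title names a test whose power at the planned size is lower than printed in 15 cells. The claim also rests on an SD limit that the reader has to extract from the table. The attrition figures are not evidence of an error; they show only how little margin the recomputed values leave. The cells printed as 85% stand 0.7 points above 80%, not 5.

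**Conclusion.** The concern holds and is minor. Table 2 is not two-sided paired t-test power at the planned n. It overstates that power in 15 of 25 cells, by at most 4.9 points. The two-sided normal approximation at n = 20 is the likelier source, but a t-test at n = 22 fits equally well, so the source is not proven. The >80% statement for 3 points holds on the grid only for SDs up to 4, and by the t-test up to about 4.5.

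The result rests on two-sided testing, which is inferred, and on 20 complete pairs. No decision rule in the plan depends on it.

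**What to change.** Recompute Table 2 from the noncentral t at n = 20, and state n and two-sided alpha in the title. Add a column or note for a smaller evaluable n, such as 16, labelled as an assumption.

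Replace the claim with wording such as: *Power for a 3-point difference exceeds 80% only if the SD of the difference is about 4.5 or less with 20 evaluable subjects (about 4.0 with 16). At SDs of 5 and 6, power with 20 evaluable is 72.1% and 56.5%, and the differences detectable with 80% power are 3.3 and 4.0 points.*

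Relabelling the table as a two-sided normal approximation at n = 20 and adding the SD limit would cure the mismatch, provided the authors confirm that this is how it was made. It would still leave figures more favourable than the t-test delivers.

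The cost is one table and one sentence, with slightly less favourable stated power. No extra patients are needed, and the design and analysis do not change.

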Joyable offers an iCBT program for Depression which is an 8-week, internet-based cognitive behavioral therapy (CBT) program for depression, developed alongside [name] PhD, a clinical psychologist with research expertise in the processes and outcomes of treatments for depression. Joyable users complete brief interactive modules (42 total activities) on a smartphone or computer. Most of these modules can be completed in 5-10 minutes and cover the core elements of CBT: psychoeducation, cognitive restructuring, and behavioral activation. In addition to its digital programs, users receive unlimited guidance and support from coaches via phone, text, and email. Coaches both respond to and proactively reach out to participants. They are trained extensively in motivational interviewing, with the goal of driving participants toward completion of the CBT program. Joyable's depression program has shown symptom reduction of 40%, as measured by the PHQ-9, with satisfaction and completion rates that exceed face-to-face therapy (unpublished data, from Joyable).

Joyable monitors the subjects' mood through weekly assessments of the PHQ-9. There are built-in escalation protocols, designed with [name], the former President of the American Association for Suicidology. Joyable identifies safety risks both through its software and through extensive training of coaches. All coaches are trained with how to respond to at-risk clients, including providing emotional support and informing clients about appropriate resources to support them, including the National Suicide Prevention Lifeline and Crisis Text Line. In urgent cases, Joyable can also connect clients with a licensed professional by phone.

Study Design

Design: A pilot single arm clinical trial is proposed. Adults (18 years or older) with ischemic stroke will be enrolled within 63 months of their event. All subjects will be enrolled in Joyable's iCBT program for Depression.

Duration: The study will plan to enroll 20 subjects. Each subject will be in the study for 90 days. The project will begin immediately after IRB approval. The study is expected to take approximately 1 year to complete.

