Joyable is a commercially available 8-week program that consists of 5-6 online activities per week, for a total of 42 activities. Most activities can be completed within approximately 5-10 minutes. Activities cover the core elements of CBT: psychoeducation, cognitive restructuring, and behavioral activation. In addition to the digital program, as a part of the Joyable product, all participants will be assigned a coach. The role of the coach is to provide accountability, motivation, emotional support, and guidance, leading clients to get the most out of the iCBT program. They provide this support through a combination of phone, text, and email interactions determined by the client. Joyable coaching is defined by 3 pillars: Motivational Interviewing (MI), Program Knowledge, and Client Experience. All coaches are trained to competency in MI, an evidence-based method for structuring conversations to harness a person's intrinsic motivation to change. MI has been shown to increase engagement and improve client outcomes. Coaches attend a rigorous 1-month training course, biweekly booster sessions, and submit tapes of client communications until they reach competency. In addition to MI, coaches are trained in the iCBT program and how to support clients with obstacles that may arise and effectively deliver program knowledge to drive client success. At the time of study enrollment, we will assist the subject in scheduling their first contact with their assigned coach.

72 Hour Telephone Encounter

Subjects will be contacted by the study team in person or by telephone 72+/- 24 hours after enrollment to troubleshoot any technical difficulties accessing the Joyable program.

30 Day Telephone Encounter

Subjects will be contacted by the study team phone or in person at 30 days +/- 7 days after enrollment to assess technical difficulties using the Joyable program, functional status using the modified Rankin scale, and quality of life using the Euroqol EQ-5D.

90 Day In-person Visit

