No clinical information obtained by the research team will be sent to Joyable. De-identified data from Joyable will be sent to the research team, which will include the number of Joyable activities completed by the subject, the number coaching interactions, and results of Joyable administered PHQ-9 and satisfaction assessments. This data will be organized by subject identification number, which can be used to link to the data collected by the research team. The research team will maintain a password protected file on a secured computer at the University of Pennsylvania which will link subject identification number to identifying information for each subject (name, medical record number, date of birth). Access to this file at the University of Pennsylvania will be limited to the PI and the study research coordinator. A Microsoft Excel document will be created which will include subject name, date of birth, and study identifier. This document will be uploaded to Penn+Box. The study team at Joyable will be given access to the file via Penn+Box. They will use this information to link the Joyable data elements described above to each subject. Joyable will then upload a Microsoft Excel file containing this data and subject identifier to the study Penn+Box, where it will be downloaded by the research team.

Patients who enroll in the study will all be participating in Joyable's iCBT Program for Depression. During enrollment in the study, patients will create an account with Joyable. As a part of this process, subjects register with Joyable using the same process as they currently use for their commercially available program. Registration requires the subject to submit the following PHI: name, date of birth, gender, and email address. Access to PHI will be limited to those who need it. This may include the individual coach who is assigned to each subject, coach managers who have access to subject data for the coaches that report to them, Joyable's analytic team which

has access to data for the purpose of aggregating and sharing back results to the research team, and a small number of engineers who can access data in order to troubleshoot bugs in the software. Subject interactions with Joyable will be governed by Joyable's existing Privacy Policy (see <https://joyable.com/privacy>) and terms of use (see <https://joyable.com/terms>).

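### The weekly PHQ-9 GEE in 20 subjects has no stated small-sample method: ordinary inference rejects 7.1% at a nominal 5% if week is linear, and far more if week is categorical

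*Combined protocol and SAP*

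**What the plan says.** There is one document, the combined protocol and SAP. Its Sample Size paragraph sets 20 subjects in a single arm.

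The Analysis Plan describes two looks at PHQ-9 change:

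- **Enrollment to day 90.** "We will compare the PHQ-9 score from enrollment to day 90". This comparison has the only power table, headed "Table 2. Statistical Power for single sample paired t-test".
- **Weekly scores.** "The PHQ-9 will also be administered to subjects weekly via through the Joyable program". The method is then given: "We will examine whether there are significant changes in score over time using repeated measures analysis (generalized estimating equations, GEE". The only detail of the model itself is that it is fitted "with PHQ-9 score as the dependent variable and week as the independent variable". Nothing further is specified for this model.

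Under Data Confidentiality, the vendor is to send the research team "results of Joyable administered PHQ-9 and satisfaction assessments". Weekly scores therefore reach the study only through the program. The plan gives no rule for weeks without a score.

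Two provisions may help keep scores coming. The Joyable section says "Coaches both respond to and proactively reach out to participants". The 30 Day Telephone Encounter includes a contact "to assess technical difficulties using the Joyable program", and a similar check is made at 72 hours.

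**The concern.** The GEE sandwich standard error is justified for many independent subjects. With 20 it is too small on average, and z or chi-square cut-offs ignore its variability. Both faults make the test too liberal. The problem grows quickly with the number of parameters tested together, so the form of week matters most.

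The weekly trend is a declared significance analysis of a primary outcome measure, and the plan does not place it among its exploratory analyses. A trend called significant would be read as preliminary evidence of efficacy. Two competent analysts could follow the same sentence and work at quite different false-positive rates. If the choice is made after the data are seen, the result could guide it.

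There is a second issue. Scores may stop when a subject disengages from the program. If stopping depends on earlier scores, the estimated trend can be biased, and the size of that bias depends on the working correlation.

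**Working it through.** **Inputs.** From the document: 20 subjects, an 8-week program, and PHQ-9 of 5-19 at entry. Assumed: two-sided 5% (alpha = 0.05 is stated only for Table 2), and 9 time points (weeks 0-8) or 8 (weeks 1-8).

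**The plan's own figure.** No error rate or power is given for the GEE. Table 2 reproduces with power = Φ(difference × √20 / SD − 1.96). For example, difference 2 and SD 3 give Φ(2.98 − 1.96) = 84.6% (stated 85%), and difference 3 and SD 5 give 76.5% (stated 77%). All 25 cells agree within 1 point. This confirms n = 20 and a two-sided 5% level, but the table says nothing about the weekly model.

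**Linear week, complete data (exact for normal scores).** Each subject has a least-squares slope. The GEE slope is the mean of these slopes, and the sandwich variance is their variance with divisor n instead of n − 1. The true SD, the true correlation, and the choice between independence and exchangeable all drop out.

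- Ordinary sandwich, z: P(|t19| > 1.960 × √(19/20)) = P(|t19| > 1.910) = **7.1%**.
- With 15 subjects: P(|t14| > 1.960 × √(14/15)) = P(|t14| > 1.894) = **7.9%**.
- Mancl-DeRouen multiplies the standard error by 20/19. With t on 18 df: P(|t19| > 2.101 × √(20/19)) = P(|t19| > 2.156) = **4.4%**.
- Interval width relative to sandwich/z: (2.101/1.960) × (20/19) = 1.128, so 13% wider.

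**Categorical week, complete data (exact).** The Wald statistic is (20/19) × Hotelling T².

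| Test | Size |
|---|---|
| Chi-square, 8 df (weeks 0-8): P(F(8,12) > 15.507 × (19/20) × 12/(8 × 19)) = P(F(8,12) > 1.163) | 39.3% |
| Chi-square, 7 df (weeks 1-8): P(F(7,13) > 1.306) | 32.1% |
| Ordinary sandwich, F(8,19) reference: P(F(8,12) > 1.486) | 25.9% |
| Mancl-DeRouen, F(8,19) reference: P(F(8,12) > 1.647) | 21.0% |

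An ordinary F reference therefore does not repair the categorical test. Exact Hotelling scaling does, but it needs complete data.

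**Stopping unrelated to scores (simulated, linear week, exchangeable).** With 43-80% still scoring at the last week, the ordinary test rejects 7.2-9.6%. The corrected test rejects 4.1-5.4%, and the low end is within simulation error of the exact 4.4%.

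**Stopping dependent on the last score (simulated, all inputs assumed).** The mean is flat at 10, the log-odds of stopping change by 0.25 per PHQ-9 point, 45% still score at week 8, and the SD of the 8-week difference is 6 (the top of Table 2's range, which concerns day 90). The results depend on how much of that variance comes from differing slopes:

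| Share from slopes | False change over 8 weeks, corrected exchangeable GEE | Rejection |
|---|---|---|
| One third | 0.45-0.48 point | 6.2-6.8% |
| Two thirds | 0.91-0.95 point | 7-8% |
| 0.9 | 1.27-1.34 points | 11-12% |

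Ranges show repeated runs.

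Separate simulations with other covariance structures and 41-46% retained gave 5.7-9.6% for corrected exchangeable. At 41-43% retained, corrected independence gave 10.6-33.4%. Doubling to 40 subjects raised the exchangeable rate to 11.3% in a random-slope case, so this excess is bias and no standard-error correction removes it.

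At the one-third share, a mixed model with random intercept and slope was biased by at most 0.06 point and rejected up to 6.8%. A random-intercept-only model rejected 13.6-14.2% even with complete data.

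**The case against.** The strongest reply is that a pilot protocol need not specify every option. The natural reading of week as one variable is a single trend term, for which the excess is only 7.1% against 5%. The weekly analysis is also secondary in position: it follows the day-90 comparison, has no stated alpha or power, and is not named as the test of the PHQ-9 primary outcome. In a single-arm study even a correctly sized test cannot attribute change to the program.

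Much of this stands, and it limits the importance of the point. It does not remove it: even on the natural reading, ordinary GEE inference is too liberal at this sample size, and the remedy costs a few sentences.

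Four stronger readings are tempting, and the documents do not support them:

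- **That the plan's test has a 39% false-positive rate.** That figure belongs to a categorical week, which the plan does not state.
- **That the corrected GEE holds 5% whatever happens.** It does so only with complete or completely-at-random scores. Nor can the remaining bias be bounded at half a point, because the documents give no slope variance.
- **That weekly scores will be lost informatively.** The documents give no rate or pattern, and the coach outreach and the 72-hour and 30-day contacts may limit loss.
- **That the PHQ-9 primary comparison is unsound for this reason.** It uses study-team scores and does not rely on the GEE.

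**Conclusion.** The concern holds, with modest impact. Ordinary GEE inference on 20 subjects gives a nominal 5% test that rejects 7.1% for linear week, 7.9% with 15 contributors, and 32-39% if week is categorical. These figures are exact for complete, normally distributed scores and need no assumed SD or correlation. The number of time points is inferred from the program length.

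The proposed correction gives about 4.4-5.4% with complete or completely-at-random scores. Under assumed heavy score-dependent stopping it can still be off by about 0.5-1.3 points over 8 weeks and reject about 6-12%. Independence is worse under such stopping. The stopping model, retention and slope variance behind these figures are assumptions.

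One further gap affects interpretation. The plan does not say which weeks enter, or whether the enrollment score serves as week 0. That score is selected to lie in 5-19, so regression to the mean could then appear as change. No standard-error correction addresses this.

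**What to change.** Keep GEE and complete the specification before the weekly data are analysed, for example:

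> The weekly trend will be estimated by GEE from the PHQ-9 scores collected by the program in all enrolled subjects, with week as one linear term, an exchangeable working correlation, a Mancl-DeRouen corrected standard error and a t reference with (subjects minus 2) degrees of freedom. The weeks included are [state], and the enrollment score [is / is not] used as week 0. Weekly means will be shown descriptively. We will report how many subjects contribute at each week and the day-90 PHQ-9 by last week scored. A REML mixed model with random intercept and random slope (Kenward-Roger or Satterthwaite degrees of freedom) will be a sensitivity analysis. The weekly trend supports the enrollment-to-day-90 comparison. Neither model removes bias if stopping follows an unobserved trend.

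Do not use a categorical-week Wald test with a chi-square or ordinary F reference, or a random-intercept-only mixed model.

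The cost is plan wording and a little analysis work, with no new data. The downsides are a 13% wider interval than sandwich/z with complete data, and less power to detect an early fall followed by a plateau.
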